3.3.1.2 Main analytical approach

Continuous secondary efficacy endpoints

Continuous secondary efficacy endpoints will be analyzed similarly as primary estimand of primary endpoint.

[figure not shown]
Percent change from baseline in total IgE in serum at Week 52

[figure not shown]
This secondary endpoint will be analyzed similarly as primary estimand of primary endpoint, and will be performed on safety population.

[figure not shown]
Proportion of participants who receive SCS and/or undergo/plan to undergo surgery for AFRS during the planned study treatment period

[figure not shown]
This secondary endpoint will be analyzed with the primary estimand defined according to the following attributes:

[figure not shown]
- Endpoint: Proportion of participants who receive SCS and/or undergo/plan to undergo surgery for AFRS during the planned study treatment period
- Treatment condition: dupilumab will be compared to placebo
- Analysis population: ITT population
- Intercurrent events (IE):
 - The following IEs will be handled with a treatment policy strategy:
 - Discontinuation of study intervention
 - Taking antifungals or other prohibited/rescue medications
- Population-level summary
 - After the implementation of IE handling strategy,
 - Missing data handling: Participant who discontinue the study prior to Week 52 without an event will be considered as no event.
 - Risk difference between interventions as well as the corresponding 95% confidence interval (CI) will be estimated using Mantel-Haenszel estimate and confidence limits, with Mantel-Haenszel stratum weights for time from last surgery (≤ 2 years, > 2 years) and region (Americas, Asia) and the Sato variance estimator. The P-value associated with Mantel-Haenszel method will be provided.
 - Descriptive statistics including number and proportion of participants with events will be provided for each intervention group.

[figure not shown]

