9.4.3 Secondary endpoint(s)

Statistical analysis methods for the secondary efficacy endpoints listed in [Table 1](#) are presented below.

The primary estimand for the secondary endpoint of proportion of participants who receive SCS and/or undergo/plan to undergo surgery for AFRS during the 52-week treatment period is the *treatment policy/while before rescue strategy*, as described in [Table 8](#).

Table 8 - Summary of primary estimand for the proportion secondary endpoint

Endpoint Category	Estimands			
	Endpoints	Population	Intercurrent event(s) handling strategy and missing data handling	Population-level summary
Secondary objective: To assess the efficacy of dupilumab to reduce the need for rescue treatments				
Secondary endpoint	Proportion of participants who receive SCS and/or undergo/plan to undergo surgery for AFRS during the 52-week treatment period.	ITT	
The following IEs will be handled with a treatment policy strategy (if without/before taking prohibited biologics):
 
 • Discontinuation of study intervention • Taking antifungals or other prohibited/rescue medications 
The following IE will be handled with a while before rescue strategy, All data before starting prohibited biologics will be included in the analysis.
 
 • Starting prohibited biologics 
In addition, the missing data imputation rules are as follows:
 
 • Discontinuing the study follow-up without an event prior to discontinuation: Participant will be considered as no event. 	Cochran-Mantel-Haenszel (CMH) test stratifying by time from last surgery (≤ 2 years, > 2 years), and region (combined countries). The estimate of the odds ratio between dupilumab and placebo will be derived.

This secondary endpoint will be analyzed using a CMH test stratifying by time from last surgery (≤ 2 years, > 2 years) and region (combined countries). All data collected after study intervention discontinuation and before starting prohibited biologics will be included in the analysis. Participants who discontinue the study follow-up without an event will be considered as no event. The estimate of the odds ratio between dupilumab and placebo will be derived with the corresponding 95% CI and p-value.

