3.8	INTERIM ANALYSES	39
3.9	CHANGES TO PROTOCOL-PLANNED ANALYSES.....	39
5	SUPPORTING DOCUMENTATION	42
5.1	APPENDIX 1 LIST OF ABBREVIATIONS	42
5.2	APPENDIX 2 PARTICIPANT DISPOSITIONS	43
5.3	APPENDIX 3 DEMOGRAPHICS AND BASELINE CHARACTERISTICS, PRIOR OR CONCOMITANT MEDICATIONS	44
5.4	APPENDIX 4 DATA HANDLING CONVENTIONS	48
5.5	APPENDIX 5 SAMPLE SAS CODE.....	51
5.6	APPENDIX 6 SELECTION CRITERIA FOR AE/MEDICATION GROUPINGS	51
6	REFERENCES.....	53

LIST OF TABLES

Table 1 - Objectives and endpoints	6
Table 2 - Summary of primary estimand for main endpoints	8
Table 3 - Populations for analyses	11
Table 4 - Sorting of AE tables	29
Table 5 - Analyses of adverse events	30
Table 6 - Selections for AESIs and other AEs of interest.....	31
Table 7 - Analyses window definition for efficacy variables	48
Table 8 - Monthly average of daily nasal symptom diary variables	49
Table 9 - Analyses window definition for safety variables.....	50
Table 10 - Analyses window definition for PK/ADA/biomarker variables	50
Table 11 - List of PTs or medications for CMQs/CDGs	51

VERSION HISTORY

This statistical analysis plan (SAP) for Study EFC16724 is based on the protocol dated 01-Mar-2023. This section summarizes the modifications made in the SAP from the Statistical Section in the protocol.

The first participant was randomized on 21-May-2021.

Modifications in statistical analysis plan

SAP Version	Approval Date	Changes	Rationale
1	22-Jan-2025	Data collected regarding the impact of COVID-19 or other pandemics on the participants will no longer be summarized.	COVID-19 or other pandemics have limited impact on study conduct currently.
		Taking prohibited biologics will not be considered as an IE for all efficacy endpoints (see Section 1.2.1, Section 3.2.2, and Section 3.3.1.2).	Prohibited biologics use is highly unlikely under the study conditions, and up to time of SAP approval there is no confirmed case of prohibited biologics use for the treatment of AFRS.
		Population-level summary of binary endpoints is changed from odds ratio based CMH method to risk difference based MH method (details in Section 3.3.2.2)	MH estimate of risk difference is more appropriate to quantify the treatment effect, compared to odds ratio from CMH method.

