- To evaluate the efficacy of treatment with dupilumab to reduce sinus opacification in a population with allergic fungal rhinosinusitis (AFRS) at Week 24
- To assess the efficacy of dupilumab to reduce the need for rescue treatments
- To evaluate the efficacy of treatment with dupilumab in improving symptoms in AFRS
- To evaluate the efficacy of dupilumab to reduce nasal polyp formation in participants with AFRS
- To evaluate the efficacy of dupilumab in improving overall symptom severity and quality of life in AFRS
- To evaluate the efficacy of dupilumab in improving sense of smell in participants with AFRS
- To explore the effect of dupilumab as assessed by three-Dimensional CT volumetric measurement of the paranasal sinuses
- To characterize the effect of dupilumab on total IgE and specific IgE

Secondary endpoint	Proportion of participants who receive SCS and/or undergo/plan to undergo surgery for AFRS during the planned study treatment period	ITT	
The following IEs will be handled with a treatment policy strategy:
 
 • Discontinuation of study intervention • Taking antifungals or other prohibited/rescue medications 	
Risk difference between interventions will be estimated using Mantel-Haenszel estimate and confidence limits, with Mantel-Haenszel stratum weights for time from last surgery (≤ 2 years, > 2 years) and region^a (Americas, Asia) and the Sato variance estimator. The P-value associated with Mantel-Haenszel method will be provided if appropriate. In addition, the missing data imputation rules are as follows:
 
 • Discontinuing the study follow-up without an event prior to discontinuation: Participant will be considered as no event.
--------------------	--	-----	---	--

Endpoint Category	Estimands			
	Endpoint	Population	Intercurrent event(s) handling strategy	Population-level summary (Analysis and missing data handling)

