3.5 MULTIPLICITY ISSUES

The multiplicity procedure is proposed to control the overall type-I error rate for testing the primary and selected secondary endpoints. The overall alpha is 0.05. The comparisons with placebo will be tested based on the hierarchical order below at 2-sided $\alpha = 0.05$:

- Change from baseline in sinus opacifications assessed by CT scans using LMK score at Week 52
- Change from baseline in monthly average nasal congestion/obstruction score from the Nasal Symptom Diary at Week 24
- Change from baseline in endoscopy NPS at Week 24
- Change from baseline in sinus opacifications assessed by CT scans using LMK score at Week 24
- Change from baseline in monthly average TSS derived from the Nasal Symptom Diary at Week 24
- Change from baseline in UPSIT at Week 24
- Change from baseline in the score of decreased/loss of smell using the Nasal Symptom Diary at Week 24
- Change from baseline in endoscopy NPS at Week 52
- Change from baseline in monthly average nasal congestion/obstruction score from the Nasal Symptom Diary at Week 52
- Change from baseline in SNOT-22 total score at Week 52
- Change from baseline to Week 52 in three-dimensional CT total volume occupied by disease in all sinuses (%)
- Proportion of participants who receive SCS and/or undergo/plan to undergo surgery for AFRS during the planned study treatment period
- Change from baseline in SNOT-22 total score at Week 24
- Percent change from baseline in total IgE in serum at Week 52

The study is considered positive when the primary endpoint achieves statistical significance with 2-sided significance level 0.05.

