3.9 CHANGES TO PROTOCOL-PLANNED ANALYSES

This section summarizes major statistical changes in the protocol amendment(s).

Major statistical changes in protocol amendment(s)

Amendment Number	Approval Date	Changes	Rationale
3	01-Mar-2023	
The sample size changed from 120 (60 per arm) to 62 (31 per arm). The updated study power is >99% for the primary endpoint and 80% for the secondary endpoint using an alpha=0.05.
 
Updated text to reflect switching of primary to secondary endpoint and vice-versa.
 
In statistical considerations, 1) primary and secondary endpoint switched, 2) stratification factor of disease pattern removed from the statistical model, and 3) intercurrent event of taking SCS for any reason changed from treatment policy to composite strategy (WOCF).
 
Alpha level of 0.01 was changed to 0.05 and study is considered positive when the primary endpoint achieves statistical significant with 2-sided significance level 0.05.
	
A sample size of 62 participants would provide ample power for the new primary endpoint based on change from baseline in LMK at Week 52, which is a clinically relevant measure of efficacy. The new sample size would allow for sufficient power for the original primary endpoint of rescue therapy utilization as a secondary endpoint.
 
The primary and secondary endpoints were switched, and the sample size was optimized based on this change. The stratification factor for disease pattern was removed from the statistical model due to only rare unilateral participants identified. The treatment policy was changed to composite strategy, an approach more appropriate for this clinical setting.
 
The alpha level was adjusted to support an optimized sample size for this rare condition.

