5.5 APPENDIX 5 SAMPLE SAS CODE

Part 1: Mantel-Haenszel method

```
proc freq data=ads;
  tables strata1*strata2*treat*bin_end / commonriskdiff (test=mh cl=mh) alpha=0.05;
  ods output CommonPdiff=mhdiff CommonPdiffTests=mhdifftest;
run;
```

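### Does the SAP's Mantel-Haenszel risk-difference test for the rescue endpoint need to be replaced by the protocol's CMH test?

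*SAP*

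**What the plan says.** Protocol 9.4.3 specifies for the rescue endpoint: "This secondary endpoint will be analyzed using a CMH test stratifying by time from last surgery", with region as the second stratifier and an odds ratio as the estimate.

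The SAP version history declares a departure: "Population-level summary of binary endpoints is changed from odds ratio based CMH method to risk difference based MH method". The reason given is that "MH estimate of risk difference is more appropriate to quantify the treatment effect, compared to odds ratio from CMH method".

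SAP 3.3.1.2 then names the MH estimate of the risk difference, MH stratum weights for time from last surgery and region, the Sato variance estimator and a 95% confidence interval, and adds that "The P-value associated with Mantel-Haenszel method will be provided". Table 2 in Section 1.2.1 has the same content but ends differently: "The P-value associated with Mantel-Haenszel method will be provided if appropriate". The sample code in Appendix 5 is a PROC FREQ call with "commonriskdiff (test=mh cl=mh) alpha=0.05".

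SAP 3.5 lists "Proportion of participants who receive SCS and/or undergo/plan to undergo surgery for AFRS during the planned study treatment period" twelfth of fourteen hypotheses, each tested at two-sided 0.05 in fixed order. SAP 3.9 records the planned power as "80% for the secondary endpoint using an alpha=0.05".

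**The concern.** Three things look wrong together. First, the reason for the change concerns the effect measure only, yet the change also replaces the hypothesis test, and the new statistic is not written as a formula. Second, Table 2 makes the p-value conditional without saying on what. A step in a fixed sequence cannot have an optional p-value: if it were withheld, the plan does not say whether steps 13 and 14 may go ahead. Third, a risk difference divided by its Sato standard error is a Wald-type test, and such tests tend to reject too often in small samples. With 31 per arm the stated 5% might be exceeded where the protocol's CMH test would have stayed nearer to it.

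At stake would be the error control of a confirmatory claim on the endpoint that was primary before Amended Protocol 03.

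**Working it through.** **1. The planned power.** The documents as supplied give no event rates, so the 80% cannot be reproduced. It can only be matched with assumed rates. With n = 31 per arm, placebo 40% and dupilumab 10%, the normal approximation is

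power = Φ{[0.30 − 1.96·√(2·0.25·0.75/31)] / √[(0.24 + 0.09)/31]} = Φ[(0.30 − 0.2156)/0.1032] = Φ(0.818) = 79.3%.

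Placebo 50% v dupilumab 17% gives 80.1%. These pairs are illustrations, not the sponsor's inputs.

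**2. Which p-value is reported.** Table 2 is introduced as a summary, with more detail in Section 3. The detailed section gives the p-value unconditionally, and Section 3.5 requires one. Read together, the three places have one workable meaning: the p-value is produced.

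**3. Whether the test is specified.** Estimator, weights, strata, variance and procedure options are all named. What is missing is the formula. The natural reading, which is an inference, is z = d/SE with

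- w = n₁n₂/N per stratum, and d = Σ[(x₁n₂ − x₂n₁)/N]/Σw
- Var(d) = [d·ΣP + ΣQ]/(Σw)²
- P = [n₁²x₂ − n₂²x₁ + n₁n₂(n₂ − n₁)/2]/N²
- Q = [x₁(n₂ − x₂) + x₂(n₁ − x₁)]/(2N)

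**4. One borderline table**, single stratum, 9 v 3 events of 31:

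- MH: d = 6/31 = 0.1935; w = 15.5; P = −1.5; Q = 318/124 = 2.5645. Var = (−0.2903 + 2.5645)/240.25 = 0.009466, SE = 0.0973, z = 1.989, p = 0.047. The 95% CI is 0.003 to 0.384.
- CMH (no continuity correction): observed − expected = 9 − 6 = 3; variance = 0.25·12·50/61 = 2.459; z = 1.913, p = 0.056.

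Of the 496 possible 31 v 31 tables favouring one given arm, the two tests disagree on significance in four: 3 v 9, 6 v 13, 18 v 25 and 22 v 28.

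**5. Type I error**, exact binomial enumeration, one stratum, 31 v 31 (%):

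| Common event rate | MH/Sato | CMH |
|---|---|---|
| 5% | 3.00 | 3.00 |
| 10% | 5.61 | 5.52 |
| 15% | 6.01 | 5.31 |
| 20% | 6.14 | 4.98 |
| 30% | 5.95 | 5.01 |
| 40% | 5.45 | 5.21 |
| 50% | 5.61 | 5.59 |

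With four strata (two by two), 62 participants, assumed stratum mixes and 400,000 simulated null trials per setting, rates of 10-50% give MH 5.5-6.1% and CMH 4.6-5.6%. The gap runs from 0.1 point (equal strata, balanced arms, 50% rate: 5.68 v 5.56) to 1.2 points (equal strata, arms not balanced within strata, 20% rate: 6.12 v 4.95).

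**6. Cost of going back to CMH.** At 40% v 10%, one stratum, exact power is 83.6% with MH and 81.3% with CMH, a loss of 2.3 points. Four-strata simulations with arms balanced within strata give about 83% v 81%.

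**The case for a change.** The best case for a change is that it is cheap and principled. The protocol named a test, the SAP's reason supports a new estimate but not a new test, and the two can be separated: keep the risk difference and Sato interval for description, and take the hierarchical p-value from CMH. That would bring the error rate closer to 5% at most assumed rates, and CMH would still have about 81% power at 40% v 10%. The borderline tables show that the choice can decide the result. Low event rates, where the MH test is conservative, are also not where the trial was planned: with no events on dupilumab, a placebo rate of 17% gives 79.7% power and 18% gives 83.4%.

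Part of this stands. The qualifier in Table 2 does no work and conflicts with Section 3.3.1.2, and a line giving the statistic would be tidier. CMH is a defensible alternative.

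The rest does not carry a change. The switch is declared with a reason, and Protocol 9.4 calls its own statistics section a summary, with the SAP to be finalised before database lock. Both tests are large-sample approximations, and CMH itself reaches about 5.6%. Separating the p-value from the interval creates a new problem: in the 9 v 3 table the report would show a 95% interval from 0.003 to 0.384 next to p = 0.056. A test that agrees with the reported estimate and interval is a reasonable choice, and statisticians differ on which property to favour.

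**Conclusion.** The concern does not call for a change. The mismatch between Table 2 and Section 3.3.1.2 is clerical: the detailed section and the hierarchy both require the p-value, so following the plan gives the same result with or without the qualifier. The unwritten formula is a detail that the named variance and the sample code fill.

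The choice of test is a fair trade-off. On the natural reading, the MH test exceeds 5% by about half a point to just over one point at event rates of 10-50%, and falls to about 3% at a 5% rate. CMH is between 0.1 and 1.2 points lower at rates of 10-50%, costs about 2 points of power, and can contradict the reported interval. Any excess matters only at step 12, after 11 rejections, with two hypotheses behind it. The primary endpoint and the criterion for a positive study are unaffected.

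These figures rest on the inferred statistic (risk difference over its Sato standard error), on CMH without continuity correction, and on assumed event rates and stratum sizes, none of which the documents give.

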3.5 MULTIPLICITY ISSUES

The multiplicity procedure is proposed to control the overall type-I error rate for testing the primary and selected secondary endpoints. The overall alpha is 0.05. The comparisons with placebo will be tested based on the hierarchical order below at 2-sided $\alpha = 0.05$:

- Change from baseline in sinus opacifications assessed by CT scans using LMK score at Week 52
- Change from baseline in monthly average nasal congestion/obstruction score from the Nasal Symptom Diary at Week 24
- Change from baseline in endoscopy NPS at Week 24
- Change from baseline in sinus opacifications assessed by CT scans using LMK score at Week 24
- Change from baseline in monthly average TSS derived from the Nasal Symptom Diary at Week 24
- Change from baseline in UPSIT at Week 24
- Change from baseline in the score of decreased/loss of smell using the Nasal Symptom Diary at Week 24
- Change from baseline in endoscopy NPS at Week 52
- Change from baseline in monthly average nasal congestion/obstruction score from the Nasal Symptom Diary at Week 52
- Change from baseline in SNOT-22 total score at Week 52
- Change from baseline to Week 52 in three-dimensional CT total volume occupied by disease in all sinuses (%)
- Proportion of participants who receive SCS and/or undergo/plan to undergo surgery for AFRS during the planned study treatment period
- Change from baseline in SNOT-22 total score at Week 24
- Percent change from baseline in total IgE in serum at Week 52

The study is considered positive when the primary endpoint achieves statistical significance with 2-sided significance level 0.05.

3.6 SAFETY ANALYSES

All safety analyses will be performed on the safety population as defined in [Section 2](#), unless otherwise specified, using the following common rules:

- The analysis of the safety variables will be essentially descriptive, and no testing is planned.
- Safety data in participants who do not belong to the safety population (eg, exposed but not randomized) will be provided separately.

3.6.1 Extent of exposure

The extent of IMP exposure will be assessed by the duration of IMP exposure and compliance and summarized within the safety population.

Duration of IMP exposure

Duration of IMP exposure is defined as last IMP administration date – first IMP administration date +14 days for adults and adolescents/children ≥ 30 kg or 28 days for adolescents/children ≥ 15 kg and < 30 kg at screening, regardless of unplanned intermittent discontinuations. If the date of the last dose of IMP is missing, the duration of IMP will be left as missing.

Duration of IMP exposure will be summarized quantitatively and categorically: 0 to 2 weeks, >2 to 4 weeks, >4 to 8 weeks, >8 to 12 weeks, >12 to 16 weeks, >16 to 20 weeks, >20 to 24 weeks, >24 to 28 weeks, >28 to 32 weeks, >32 to 36 weeks, >36 to 40 weeks, >40 to 44 weeks, >44 to 48 weeks, >48 to 52 weeks +3 days, >52 weeks +3 days.

Additionally, the cumulative duration of treatment exposure (expressed in participant-years) will be provided.

Treatment compliance

A given administration will be considered noncompliant if the participant did not take the planned dose as required by the protocol. No imputation will be made for participants with missing or incomplete data.

Percentage of treatment compliance for a participant will be defined as the number of administrations that the participant was compliant divided by the total number of administrations that the participant was scheduled to take from the first administration of IMP up to the actual last administration of IMP.

Treatment compliance will be summarized quantitatively and categorically: <80%, $\geq 80\%$.

Cases of symptomatic overdose (defined as at least twice the intended dose during an interval of less than 11 days for adults and adolescents/children ≥ 30 kg at screening or less than 25 days for adolescents/children ≥ 15 kg and < 30 kg at screening) are required to be reported as AESIs and will be listed as such.

3.6.2 Adverse events

General common rules for adverse events

All adverse events (AEs) will be coded to a lower-level term (LLT), preferred term (PT), high-level term (HLT), high-level group term (HLGT), and associated primary system organ class (SOC) using the Medical Dictionary for Regulatory Activities (MedDRA) version currently in effect at Sanofi at the time of database lock.

The AEs will be analyzed in the following 3 categories:

- Pre-treatment AEs: AEs that developed, worsened or became serious during the pre-treatment period.
- Treatment-emergent adverse events (TEAE)s: AEs that developed, worsened or became serious during the treatment-emergent period.
- Post-treatment AEs: AEs that developed, worsened or became serious during the post-treatment period.

Similarly, the deaths will be analyzed in the pre-treatment, treatment-emergent and post-treatment periods.

The primary AE analyses will be on TEAEs. Pre-treatment and post-treatment AEs will be described separately.

An AE with incomplete or missing date/time of onset (occurrence, worsening, or becoming serious) will be classified as a TEAE unless there is definitive information to determine it is a pre-treatment or a post-treatment AE.

If the assessment of the relationship to IMP is missing for an AE, this AE will be assumed as related to IMP. Missing severity will be left as missing.

Multiple occurrences of the same event in the same participant will be counted only once in the tables within a treatment phase.

The AE tables will be sorted as indicated in [Table 4](#).

Table 4 - Sorting of AE tables

AE presentation	Sorting rules
SOC, HLGT, HLT and PT	By the internationally agreed SOC order and by alphabetic order of HLGTs, HLTs and PTs.
SOC, HLT and PT	By the internationally agreed SOC order and by alphabetic order of HLTs and PTs.
SOC and PT	By the internationally agreed SOC order and decreasing frequency of PTs ^{a,b}
SMQ/CMQ and PT	By decreasing frequency of SMQs/CMQs and PTs ^a
PT	By decreasing frequency of PTs ^a

^a Sorting will be based on the dupilumab intervention group.

^b The table of all TEAEs presented by primary SOC and PT will define the presentation order for all other tables (eg, treatment-emergent SAE) presented by SOC and PT, unless otherwise specified.

Analysis of all adverse events

The overview of TEAE with the details below will be generated:

- Any TEAE
- Any severe TEAE

- Any treatment-emergent SAE
- TEAE leading to death
- Any TEAE leading to permanent intervention discontinuation
- Any treatment-emergent AESI
- Any treatment-emergent other AE of interest grouping
- Any TEAE related to IMP

The AE summaries of **Table 5** will be generated with number (%) of participants experiencing at least one event. A separate analysis of TEAE by primary SOC and PT will be provided for pediatric patients.

Table 5 - Analyses of adverse events

Type of AE	MedDRA levels
All TEAE	Primary SOC, HLGT, HLT and PT
	Primary SOC and PT
	Primary SOC
	PT
Common TEAE ($\geq 5\%$ in any group)	Primary SOC and PT
TEAE related to IMP as per Investigator's judgment	Primary SOC, HLGT, HLT and PT
	Primary SOC and PT
TEAE by maximal intensity	Primary SOC and PT
Treatment emergent SAE	Primary SOC, HLGT, HLT and PT
	Primary SOC and PT
Treatment emergent SAE related to IMP as per Investigator's judgment	Primary SOC and PT
TEAE leading to permanent intervention discontinuation	Primary SOC, HLGT, HLT and PT
	Primary SOC and PT
TEAE leading to death ^b	Primary SOC, HLGT, HLT and PT
	Primary SOC and PT
Pretreatment AE	Overview ^a
	Primary SOC and PT
Post-treatment AE	Overview ^a
	Primary SOC and PT
Post-treatment SAE	Primary SOC and PT

^a Will include the following AE categories: any AEs, any serious AEs, any AEs leading to death, any AEs leading to permanent intervention discontinuation

^b Death as an outcome of the AE as reported by the Investigator in the AE page

Analysis of deaths

In addition to the analyses of deaths included in Table 5 the number (%) of participants in the following categories will be provided:

- Deaths during the treatment-emergent and post-treatment periods by main reason for death
- Deaths in non-randomized participants or randomized but not treated participants

Analysis of adverse events of special interest (AESIs) and other AEs of interest

Adverse events of special interest (AESIs) and other AEs of interest will be selected for analyses as indicated in [Table 6](#). Number (%) of participants experiencing at least one event will be provided for each event of interest, by PT if applicable. Tables will be sorted as indicated in [Table 4](#).

Table 6 - Selections for AESIs and other AEs of interest

AESIs and other AEs of interest	Selection
AESI	
Anaphylactic reaction	Anaphylactic reaction algorithmic approach (Introductory Guide for Standardized MedDRA Queries (SMQs) Version 18.1): includes anaphylactic reaction narrow SMQ (20000021) terms and programmatic identification of cases based on occurrence of at least two preferred terms meeting the algorithm criteria occurring within 24 hours of each other. The latter cases identified using the algorithm will undergo blinded medical review taking into account the timing of events relative to each other and to IMP administration for final determination of an anaphylactic reaction or not.
Systemic hypersensitivity reactions	SMQ [20000214] hypersensitivity narrow search and [AE corrective treatment/therapy = 'Y' or Action taken with IMP = 'Drug withdrawn' or Action taken with IMP = 'Drug interrupted'] followed by blinded medical review (documented process) for selection of relevant systemic hypersensitivity events
Helminthic infections	CMQ10544 based on HLGT as "Helminthic disorder"
Any severe type of conjunctivitis	CMQ10498 based on PTs (See Appendix 6) ^a and "Severe" ticked in Adverse Events eCRF page
Any severe type of blepharitis	CMQ10497 based on HL as "Lid, lash and lacrimal infections, irritations and inflammations" and "Severe" ticked in Adverse Events eCRF page
Keratitis	CMQ10642 based on the following PTs [keratitis, allergic keratitis, ulcerative keratitis, atopic keratoconjunctivitis, herpes ophthalmic, ophthalmic herpes simplex, corneal infection] ^a
Clinically symptomatic eosinophilia (or eosinophilia associated with clinical symptoms) ^b	CMQ10641 based on HL = Eosinophilic disorders or PT = Eosinophil count increased followed by blinded medical review
Pregnancy of female participants entered in a study as well as pregnancy occurring in a female partner of a male participant entered in a study with IMP	"Pregnancy" or "Partner Pregnancy" checked on the Pregnancy eCRF page as reported by the investigator

AESIs and other AEs of interest	Selection
Significant ALT elevation	"ALT increase" and AESI answer "Yes" checked on AE eCRF as reported by the Investigator (ALT >5 × ULN in participants with baseline ALT ≤2 × ULN; OR ALT >8 × ULN if baseline ALT >2 × ULN)
Symptomatic overdose with IMP	Symptomatic Overdose is answered Yes, with Overdose of Study Treatment answered Yes on AE eCRF.
Other selected AE Grouping	
Serious injection site reactions or severe injection site reactions that last longer than 24 hours	HLT = 'Injection site reactions' and either with serious status, or with severe status and (AE end date/time - AE start date/time) ≥24 hours or ongoing
Severe or serious infection	Primary SOC = 'Infections and infestations' and with severe or serious status
Parasitic infection	Infection type "Parasitic" checked on eCRF "Infection Event Form"
Opportunistic infection	Has the AE been assessed as opportunistic infection? is answered Yes on eCRF "Infection Event Form"
Drug-related hepatic disorder	SMQ [20000006] Drug-related hepatic disorders- narrow
Injection site reactions	HLT = 'Injection site reactions'
Malignancy	SMQ [20000091]- Malignant or unspecified tumors narrow
Conjunctivitis (narrow)	CMQ10644 based on the following PTs [Conjunctivitis, Conjunctivitis allergic, Conjunctivitis bacterial, Conjunctivitis viral, Atopic keratoconjunctivitis] ^a
Conjunctivitis (broad)	CMQ10645 based on the following PTs [Conjunctivitis, Conjunctivitis allergic, Conjunctivitis bacterial, Conjunctivitis viral, Atopic keratoconjunctivitis, Blepharitis, Dry eye, Eye irritation, Eye pruritus, Lacrimation increased, Eye discharge, Foreign body sensation in eyes, Photophobia, Xerophthalmia, Ocular hyperaemia, Conjunctival hyperaemia] ^a
Conjunctivitis (FDA) ^c	CMQ10643 based on the following PTs [Conjunctivitis, Conjunctivitis allergic, Conjunctivitis bacterial, Conjunctivitis viral, Eye irritation, Eye inflammation, Giant papillary conjunctivitis] ^a
Keratitis (FDA) ^c	CMQ30102 based on the following PTs [keratitis, allergic keratitis, ulcerative keratitis, atopic keratoconjunctivitis, ophthalmic herpes simplex] ^a

a The list of terms may be adjusted according to MedDRA version changes

b All cases of Eosinophilia will be included in the analysis, where cases associated with clinical symptoms will be further described in the CSR

c Labeling subgroup of preferred terms included in the USPI for Dupixent.

The following summaries will be provided:

- All TEAEs, by selected standardized MedDRA query (SMQ)/Customized MedDRA query (CMQ) and PT, showing the number (%) of participants with at least 1 PT.
- For each AESI and other selected AE groupings,
 - Number (%) of participants with any TEAE
 - Number (%) of participants with any serious AE (regardless of treatment-emergent status)

- Number (%) of participants with any treatment-emergent serious AE
- Number (%) of participants with any AE leading to death
- Number (%) of participants with any TEAE leading to permanent study intervention discontinuation
- Number (%) of participants with any TEAE related to IMP reported by investigator
- Number (%) of participants with any TEAE by maximum intensity, corrective treatment, and final outcome
- Number (%) of participants with any TEAE adjusted by the exposure duration
- Number (%) of participants with injection site reactions by the related injection.
- Number (%) of participants with different number of injection site reactions.

In addition, AESIs reported by the investigator in eCRF will be summarized separately.

Analysis of exposure-adjusted incidence rate

If the cumulative duration of treatment exposure is imbalanced between dupilumab and placebo, then the number of participants with at least one TEAE per 100 participant-years will be provided for the below summaries:

- Overview of adverse events profile
- TEAE by primary SOC and PT
- Common TEAE ($\geq 5\%$ in any group) by primary SOC and PT
- Treatment-emergent SAE by primary SOC and PT
- TEAE leading to permanent intervention discontinuation by primary SOC and PT
- Treatment-emergent AESI and other selected AE grouping events by category and PT

For participants with an event, the number of participant-years will be censored at time of the first event; for participants without an event, the number of participant-years corresponds to the length of the treatment-emergent period.

